1 PROTOCOL SYNOPSIS

Title	Partial Responders to PPI treatment: the Cost to Society and the Burden to the Patient – a study in France (REMAIN Study –French Arm)
Protocol Number	Study code D9120N00013
Study design	French arm of a multi-center, prospective, observational, non interventional study
Patients	Patients with Gastroesophageal Reflux Disease (GERD) newly classified as partial-responders to proton pump inhibitors (PPIs)
Period for Patient Participation	
Primary objectives	
– To describe common treatment pathways, including extent of and time to referral to specialists;– To collect resource utilization data;– To collect relevant cost estimates and calculate cost per patient;– To assess the symptom load, impact of symptoms on daily life and effect on work productivity.
Secondary objectives	
– To estimate the proportion of new partial-responders to all new patients with GERD
Inclusion criteria	
1. Provision of signed informed consent.2. Able to read and write in French and able to comply with study requirements.3. Female or male, aged 18 years or above.4. The patient must at the enrolment visit be identified for the first time as partial responder to PPI treatment as defined by the following criteria:
a) At least 6 month history of GERD symptoms (need not be consecutive)b) Continuously treated with unchanged optimized PPI treatment for any GERD indication during the last 4 weeks (an optimized PPI treatment is a treatment, which according to the investigators judgment cannot be further improved by changing brand or dosing of the PPI) .c) Patients with a history of reflux (erosive) esophagitis Los Angeles grade A-D must have been continuously treated with a PPI during the last 8 weeks before enrolment (optimized PPI treatment during the last 4 weeks before enrolment).

	
5. To be eligible for enrolment, the patients must have reported, in the RDQ-RI screening instrument using 7 days recall, a minimum of three days with at least one of the two following symptoms with at least moderate severity:
 
 • a burning feeling behind the breastbone • an unpleasant movement of material upwards from the stomach.

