Exclusion criteria	
 1. Patients that have not experienced any GERD symptoms improvement at all during PPI treatment. 2. Prior surgery of the upper GI tract (open, endoscopic and laparoscopic surgery on the esophagus, the stomach and the duodenum with the exception of over sewing or endoscopic treatment of an bleeding ulcer) 3. Any other condition which in the opinion of the investigator would render the patient unsuitable for inclusion in the study. 4. Involvement in the planning or conduct of the study. 5. Previous enrolment in the present study. 6. Involvement in any other observational study or in any clinical study at the time of this study or during the last 6 months.
Primary and secondary endpoints	
Frequency and severity of GERD symptoms
 
Quality of Life
 
Productivity loss
 
Healthcare resource use (primary care visits, secondary care visits, medications, diagnostic tests, surgeries, etc.)
 
Utility values

Patient-reported Outcome Instruments	
Reflux Disease Questionnaire – Reflux Inhibition (RDQ-RI)
 
GERDQ
 
Quality of Life in Reflux and Dyspepsia – Reflux Inhibition (QOLRAD-RI)
 
EQ-5D
 
Short Form 36 (v2)
 
HADS
 
Work Productivity and Activity Impairment for Patients with Gastroesophageal Reflux Disease (WPAI-GERD)
 
Resource Utilization Questionnaire

Sample size	275 enrolled partial-responders to PPI for the treatment of GERD (200 completed subjects)
Procedures	Patients will be recruited by their physicians during a regularly scheduled office visit. The physician will recruit patients into the study who are

	
identified for the first time as partial responders to PPI treatment. Patients will be asked to complete a self-administered questionnaire at the recruitment visit and every 3 months for a total period of 12 months thereafter. Follow-up questionnaires will be sent to the patient's place of residence. Physicians will collect the patient's medical history, demographics and co morbidities in a paper CRF at the recruitment visit and will collect information from medical records on health resource use every 6 months for a total of 12 months per patient. In addition, the physician will keep a log of all new patients with GERD seen at their office during the enrollment period in order to allow for an estimate of the ratio of partial responders to all new patients with GERD.

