3.2 Secondary Objective

The secondary objective of this study is to estimate the proportion of patients with GERD being identified for the first time as partial responders to optimized PPI treatment, to all patients newly diagnosed with GERD.

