5 SUBJECT POPULATION

The target population for this study is adults, aged 18 and older, who are suffering from GERD and are newly diagnosed as partial responder to optimized PPI treatment. Subjects must meet all of the following inclusion criteria to be eligible for enrollment into the study:

Inclusion Criteria:

1. Provision of signed informed consent.
2. Able to read and write in French and able to comply with study requirement.
3. Female or male, aged 18 years or above.
4. The patient must at the enrolment visit be identified for the first time as partial responder to PPI treatment as defined by the following criteria:
 - a) At least 6 month history of GERD symptoms (need not be consecutive)
 - b) Continuously treated with unchanged optimized PPI treatment for any GERD indication during the last 4 weeks (an optimized PPI treatment is a treatment, which according to the investigators judgment cannot be further improved by changing brand or dosing of the PPI) .
 - c) Patients with a history of reflux (erosive) esophagitis Los Angeles grade A-D must have been continuously treated with a PPI during the last 8 weeks before enrolment (optimized PPI treatment during the last 4 weeks before enrolment).
5. To be eligible for enrolment, the patients must have reported, in the RDQ-RI screening instrument using 7 days recall, a minimum of three days with at least one of the two following symptoms with at least moderate severity:
 - a burning feeling behind the breastbone
 - an unpleasant movement of material upwards from the stomach.

Exclusion Criteria:

1. Patients that have not experienced any GERD symptoms improvement at all during PPI treatment.
2. Prior surgery of the upper GI tract (open, endoscopic and laparoscopic surgery on the esophagus, the stomach and the duodenum with the exception of over sewing or endoscopic treatment of an bleeding ulcer)

-
3. Any other condition which in the opinion of the investigator would render the patient unsuitable for inclusion in the study.
 4. Involvement in the planning or conduct of the study.
 5. Previous enrolment in the present study.
 6. Involvement in any other observational or clinical study at the time of this study.

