7.3 Subject Recruitment

Subjects will be recruited in community practice settings by approximately 50 study physicians in France. The target recruitment goal for each physician is 5 to 6 patients with GERD newly identified as partial responders with an upper limit of 14 per physician. Subjects will be enrolled during a normally scheduled office visit.

Enrollment will be closed once the target enrollment goal of 275 patients has been reached. Study physicians will be notified by telephone and fax memo that recruitment is closed.

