7.7 Log of new GERD patients

A log of all newly diagnosed patients with GERD seen in the physician's office will be maintained during the duration of patient enrollment. This paper-based log will contain the following data fields to allow for the estimate of a ratio of all newly diagnosed patients with GERD and first time partial responders:

- Patient year of birth
- Patient gender
- Date of first GERD diagnosis / Date seen in Practice

This log will be returned to i3 at the end of enrollment period. A copy of the log will be kept on site.

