10.2 Study Population

Two study populations are considered: the “log population”, which consists of all GERD patients approached for this study and the “per protocol population”, which consists of all patients enrolled in the study, satisfying to inclusion and exclusion criteria specified in section 5.

The proportion of partial-responders to PPI and analysis of screening failure will be conducted over the log population and the analyses of symptoms, patients reported outcomes, healthcare

resource use, productivity loss and associated costs will be performed on the per protocol population.

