10.7 Cost of Illness Analysis

The first step of this analysis will consist of estimating the size of the target population. A literature review will be undertaken to obtain the incidence and prevalence of GERD in France and the proportion of patients treated in primary care and secondary care. The proportion of

patients with GERD with incomplete response to PPI will be calculated from the sites' log. The proportion of partial responders will be reported by site, physician type and overall, together with 95% confidence intervals. The size of the target population (partial responders to PPI) in France will then be derived.

Based on the information obtained from the cost of healthcare resources collected alongside this study, we will be able to estimate the cost of partial response to PPI within the year of partial response diagnosis. Some assumptions will be made on the basis of the literature and clinical experts' opinion to estimate the mean cost of treatment over subsequent years. The cost of partial response to PPI will be reported overall and by type of resource (GP visits, specialist visits, diagnostic tests, hospitalization, prescribed medications and OTC medications) for France.

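### The secondary objective, new partial responders relative to newly diagnosed GERD patients, is not identified: the denominator is defined in two ways, the log does not record the numerator, and the quantity is a ratio rather than a proportion

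*Protocol*

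**What the plan says.** **Objective.** The synopsis gives the secondary objective as "To estimate the proportion of new partial-responders to all new patients with GERD". Section 3.2 also speaks of a proportion and relates first-time partial responders "to all patients newly diagnosed with GERD". The synopsis procedures instead promise an "estimate of the ratio of partial responders to all new patients with GERD", and sections 4 and 7.7 also call it a ratio.

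**Log.** Under section 7.7 each practice lists its newly diagnosed GERD patients for as long as enrolment lasts. The fields are year of birth, gender and "Date of first GERD diagnosis / Date seen in Practice".

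**Analysis population.** Section 10.2 defines the log population as one "which consists of all GERD patients approached for this study", and assigns to it both the proportion of partial responders and the analysis of screening failures.

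**Use.** Section 10.7 states that the proportion of "patients with GERD with incomplete response to PPI will be calculated from the sites" (their logs). It is to be reported by site, by physician type and overall with 95% confidence intervals. Together with incidence and prevalence from the literature, it then yields the size of the French target population.

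**Who is a partial responder.** Section 5, criterion 4, requires a symptom history of at least 6 months and, at 4b, "Continuously treated with unchanged optimized PPI treatment for any GERD indication during the last 4 weeks". Patients with a history of erosive esophagitis need 8 weeks of PPI.

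**The concern.** Three things needed for an estimate are unsettled.

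- **Denominator.** Newly diagnosed patients and approached patients are different groups. Under section 7.4 the physician tries to recruit a patient only after judging that patient to be a first-time partial responder. The section 10.2 denominator therefore measures the yield of screening among suspected cases, not how often partial response arises relative to new diagnoses.
- **Numerator.** The log is named as the source but cannot show who is a partial responder. Nothing in the protocol records partial responders who decline.
- **Type of quantity.** The two groups barely overlap, so the result is not a share of the denominator.

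This is the only secondary objective and the multiplier for the national target population. An error in it passes in full proportion to that population. A later analysis plan can choose a formula, but it cannot supply patients whom nobody recorded.

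**Working it through.** The protocol states no expected value, log size or precision for this quantity, so there is no figure to reproduce. The log size D and the consent rate c below are assumptions.

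**1. The two denominators.** Take one site with 20 newly diagnosed patients, 8 approached and 5 enrolled (all assumed).
- Denominator of sections 3.2 and 7.7: 5/20 = 25%.
- Denominator of section 10.2: 5/8 = 62.5%.

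The same site gives two answers that do not estimate the same thing.

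**2. What the log can supply.**

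| Needed | In the log (7.7)? | Elsewhere? |
|---|---|---|
| New diagnoses | Yes | – |
| Partial-responder status | No | CRF, consented patients only |
| Approached for the study | No | Not recorded |
| Declined | No | Not recorded |
| Ineligible after consent | No | Baseline CRF pages (7.4) |

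**3. Overlap of the groups.** Criterion 4b needs 4 weeks of optimized PPI before the visit. A patient first diagnosed at today's visit will normally not qualify. If the groups are disjoint, with P partial responders and D new diagnoses, the ratio is R = P/D and the share of the combined group is P/(P + D). With P = 275:

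| D (assumed) | R = 275/D | 275/(275 + D) |
|---|---|---|
| 250 | 1.10 | 0.524 |
| 500 | 0.55 | 0.355 |
| 1000 | 0.275 | 0.216 |
| 2000 | 0.138 | 0.121 |

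At D = 250 the so-called proportion is above 1. At D = 500 the two readings are 0.55 and 0.355.

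**4. Effect of counting only consented patients.** If enrolled = c × identified, then R(observed)/R(true) = c, and the understatement is 1 − c.
- c = 0.8: 1 − 0.8 = 20% too low.
- c = 0.5: 1 − 0.5 = 50% too low.
- c = 0.6 with D = 500: the true R is (275/0.6)/500 = 0.917, against 0.55 observed.

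**5. Effect of the cap.** Recruitment is "with an upper limit of 14 per physician". The mean per recruiting unit is 275/50 = 5.5 with the 50 physicians of section 7.3, or 275/30 = 9.17 with the 30 sites of section 4. The share retained is E[min(X, 14)]/E[X], with X the uncapped count per unit under assumed distributions:

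| Mean | Poisson | Negative binomial, k = 2 | Negative binomial, k = 1 |
|---|---|---|---|
| 5.5 | 100% | 96% | 90% |
| 9.17 | 99% | 86% | 77% |

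The cap matters only if recruitment is very uneven or few sites take part.

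**The case against.** The best defence is that the protocol already calls the quantity a ratio in three places (synopsis procedures, sections 4 and 7.7). A ratio of two flows over one time window can be computed and interpreted, and the method for the interval belongs to the analysis plan. The first two parts of this are right. The remedy below is that same ratio, properly sourced. But sections 3.2, 10.2 and 10.7 say proportion, section 10.2 changes the denominator, and the numerator stays unnamed and partly unrecorded.

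Several stronger readings are tempting but not supported:

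- **Closure at 275 biases the ratio.** Section 7.7 keeps the log during enrolment and has it returned when enrolment ends. Numerator and denominator therefore stop together.
- **The cap seriously cuts the numerator.** Fourteen is well above the target of 5 to 6 per physician, and the effect is small in most settings tried above.
- **Reasons for exclusion are lost.** Section 7.4 collects baseline CRF pages for patients who fail eligibility. What is missing is a record of those who decline.
- **Partial responders are never in the denominator.** A patient diagnosed early in enrolment may qualify later. Section 2 also notes that diagnosis often follows response to acid suppression, so treatment can come before it.
- **The national figure will be many times too large because the ratio is applied to prevalence.** Section 10.7 obtains both incidence and prevalence and does not say which is multiplied. Its costing of the year of partial response diagnosis fits incidence. The text is ambiguous but does not state a misuse.
- **The confidence interval is invalid.** No method is given, so this cannot be said.

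**Conclusion.** The point holds in this form: followed as written, the plan does not identify its secondary objective or give a sound multiplier for the French target population. The conflicting log definitions, the missing responder field and the unnamed numerator rest on the protocol's text alone.

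The size cannot be fixed from the document. The understatement of 20–50% assumes that consented patients are the numerator and that 50–80% consent. The value of 1.10 assumes 250 logged patients and 275 enrolled. It is not shown that the national figure will be wrong by any particular amount, only that it would be undefined and probably biased low if refusals go uncounted.

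A reader might infer that the cost results fail as a whole. They do not: cost per patient and the other primary objectives do not use the log, and a national cost of illness is not among the listed objectives.

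**What to change.** 1. **Section 10.2:** define the log population as in section 7.7, the newly diagnosed GERD patients seen during enrolment. Give approached patients their own name for the analysis of screening failures.
2. **Section 7.7:** add one log line for each patient first identified as a partial responder, with a status (enrolled, declined, ineligible). Complete it whether or not the patient enrols, and also after a site reaches its cap. For patients who decline, identification must rest on the physician's judgement, because section 7.4 allows no study procedure, and so no RDQ-RI, before consent. State this.
3. **Sections 3.2, 10.2 and 10.7 and the synopsis:** report R = all first-time partial responders identified / all newly diagnosed GERD patients, over the same window at each site. Call it a ratio throughout.
4. **Section 10.7:** give the overall and physician-type ratios a 95% confidence interval that treats site as the unit, for example a ratio estimator or a bootstrap over sites. Show the two counts for each site.
5. **Section 10.7:** state that R multiplies incidence, not prevalence.
6. Reconcile the 30 sites of section 4 with the 50 of sections 7.1 and 7.3, since this sets the number of units for the interval.

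**Cost:** more recording at the sites, namely a second stream of patients and a status for each, and notification of the amendment to CCTIRS and CNIL under section 14.1. The change must be made before enrolment starts, because partial responders who were not logged cannot be counted later.

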11 ETHICAL & REGULATORY CONSIDERATION

11.1 Comité Consultatif sur le Traitement de l'Information en matière de Recherche dans le domaine de la Santé (CCTIRS)

Unlike an interventional clinical study, this observational non interventional study does not require a submission to Health authorities and Ethics Committees. However, the study will be performed in accordance with ethical principles that have their origin in the Declaration of Helsinki and are consistent with applicable parts of ICH/Good Clinical Practice.

In accordance to applicable law, this protocol will be submitted for evaluation to CCTIRS for opinion and recommendation on study methodology and review of the study's compliance with local laws for the protection of personal data.

11.2 Commission Nationale Informatique et Liberté (CNIL)

Following the process of CCTIRS and in accordance with the data protection law the protocol as well as patient information and the consent form are submitted to the CNIL for approval.

The informed consent form will integrate the reference to the specific law and inform the patient on his rights regarding the personal data collected during the course of the study.

11.3 Conseil National de l'Ordre des Médecins (CNOM)

The physician will receive compensation for his participation in this trial. This compensation will be clearly detailed in a financial agreement that will form part of the site contract. The site

contract will be submitted to the CNOM for their opinion. In addition, the physician will be responsible to inform his local council about his participation in the trial and corresponding compensation.

11.4 Regulatory considerations

The study is designed to follow Good Epidemiology Practice (GEP Guidelines) and the applicable parts of the Good Clinical Practice standards as set forth in the ICH Harmonized Tripartite Guideline for Good Clinical Practice (GCP Guidelines), the International Conference on Harmonization of Technical Requirements for Registration of Pharmaceuticals for Human Use (ICH) as identified below:

- 2.3 The rights, safety, and well-being of the trial subjects are the most important considerations and should prevail over interests of science and society
- 2.9 Freely given informed consent should be obtained from every subject prior to clinical trial participation
- 4.8 Informed Consent of Trial Subjects

In addition, the study will run in accordance with the applicable SOPs as outlined in detail in the project plan.

12 PRIVACY AND SECURITY

The collection and processing of personal data from patients enrolled in this study will be limited to those data that are necessary to investigate the outcomes identified for this study and will be in compliance with applicable data privacy protection laws and regulations.

Explicit consent for the processing of personal data will be obtained from the participating patient before collection of data. Such consent will also address the transfer of the data to other entities, including the sponsor, doctors and healthcare professionals taking part in the study.

13 EARLY TERMINATION OF STUDY

Premature termination of this study may occur because of a regulatory authority decision, change in opinion of the Committee, or at the discretion of AZ.

If a study is prematurely terminated or discontinued, AZ or its contracted agents will promptly notify each study physician. After notification, participating subjects will be contacted within ten (10) days. As directed by AZ, all completed study materials must be collected and all CRFs

completed to the greatest extent possible. Any unused study materials will be destroyed by investigators.

14 ADMINISTRATIVE AND LEGAL OBLIGATIONS

14.1 Protocol amendments

Protocol amendments must be reviewed and approved by AZ. Agreement from i3 must be obtained for all protocol amendments and amendments to the ICF. The CCTIRS and CNIL must be informed of all amendments and give approval for any amendments likely to affect the safety of the patients or the conduct of the study. i3 will send a copy of the written approval from the committees to AZ.

14.2 Study termination

AZ reserves the right to terminate the study. i3 will notify each sites' study coordinator of the termination of the study.

If a study is prematurely terminated or discontinued, AZ or its contracted agents will promptly notify each study physician. After notification, participating subjects will be contacted by the physician. As directed by AZ, all completed study materials must be collected and all CRFs completed to the greatest extent possible. Any unused study materials will be destroyed by investigators.

14.3 Study documentation and storage

Source documents are original documents, data, and records from which the subject's data are obtained. Case report form and other survey instrument entries may be considered source data if the CRF or other survey instrument is the site of the original recording (i.e., there is no other written or electronic record of data).

i3 will maintain a comprehensive and centralized filing system of all study related (essential) documentation per i3's Study Master File (SMF) SOP, suitable for inspection at any time by representatives from AZ.

Study-related documentation includes patient files containing completed CRFs, supporting copies of source documentation, regulatory files containing the protocol with all amendments, all ICFs, all survey instruments and all correspondence to and from the Committees and AZ.

